18.3. PK ANALYSIS

PK analyses will be carried-out by Accelera using Phoenix WinNonlin 6.3 (Certara Company).

For both **Part A and B**, PK parameters of Givinostat and its metabolites (ITF-2374 and ITF-2375) will be: C_{max}, C_{last}, CT_{max}, AUC_{last} and if data permit and only for Givinostat AUC(0- τ), R_o (observed accumulation ratio on C_{max}, AUC_{last} and if data permit AUC(0- τ)) and Ratio ITF-2374 parent or ITF-2375/parent C_{max} and AUC_{last}.

The actual plasma sampling times will be used in the analysis.

For the PK calculation, plasma concentrations below the lower limit of quantification (BLQ) will be treated as follows:

- All BLQ values before the first detectable concentration will be set equal to zero.
- All BLQ values after the last detectable plasma concentration will be excluded .
- BLQ value between two detectable plasma concentrations will be excluded.

For the descriptive statistic calculation on plasma concentration data, the BLQ values will be treated as follows:

- BLQ values will be set equal to zero.
- BLQ values between two detectable plasma concentrations will be excluded.

Individual values considered to be anomalous will be excluded from the pharmacokinetic analysis and descriptive statistics. Justification for exclusion will be provided in the pharmacokinetic report.

Document: PPD

Author: PPD

Version Number:

V2.2

Version Date:

21 March 2018

Template No: CS_TP_BS016 – Revision 3

Reference: CS_WI_BS005

Effective Date: 01May2012

Copyright © 2012 Quintiles Transnational Corp. All rights reserved.

The contents of this document are confidential and proprietary to Quintiles Transnational Corp. Unauthorized use, disclosure or reproduction is strictly prohibited.

The following PK plasma parameters will be calculated for **both part A and B**:

- Tmax,
- Tlast,
- Cmax,
- Clast,
- C τ ,
- AUClast

and if data permit AUC(0- τ) and Ro (observed accumulation ratio on Cmax and AUClast and if data permit AUC(0- τ)) between the individual parameter obtained on Day 28 to the corresponding one on Day 1.

Pharmacokinetic parameters will be calculated as follows:

- Tmax,
- Tlast,
- Cmax,
- Clast

and C τ will be taken directly from the raw data.

Areas under the plasma concentration vs. time curve (AUClast, AUC(0- τ)) will be calculated using linear trapezoidal rule.

Accumulation ratios Ro on Cmax, AUClast and if data permit on AUC(0- τ) will be calculated as the ratio between the individual parameter obtained on Day 28 to the corresponding one on Day 1. Ratios between metabolites (ITF-2374 and ITF-2375) to parent drug will be performed on Cmax and AUClast on day 1 and day 28.

Descriptive statistics of plasma concentrations and pharmacokinetic parameters of Givinostat will include N, Mean, SD, Coefficient of Variation (CV) Median, Minimum, and Maximum.

The following units will be used for individual and mean parameters of the compound:

- Cmax, Clast, C τ : ng/mL,
- Tmax, Tlast: hr,
- AUCs: ng·hr/mL.

Descriptive statistics of plasma concentrations and pharmacokinetic parameters of Givinostat will include N, Arithmetic Mean, SD, Geometric Mean, Coefficient of Variation (%), Min, Median and Max.

Document: PPD

Author: PPD

Version Number:

V2.2

Version Date:

21 March 2018

Template No: CS_TP_BS016 – Revision 3

Reference: CS_WI_BS005

Effective Date: 01May2012

Copyright © 2012 Quintiles Transnational Corp. All rights reserved.

The contents of this document are confidential and proprietary to Quintiles Transnational Corp. Unauthorized use, disclosure or reproduction is strictly prohibited.

Appropriate statistical methods will be applied to analyze accumulation ratio (R0) and dose proportionality.

In particular, to estimate the extent of accumulation after repeat dosing, the observed accumulation ratio will be determined using Cmax and AUClast and if data permit AUC(0- τ) log-transformed values.

A mixed effect model will be implemented with day as fixed effect and patient as a random effect. Day 28 will be compared vs Day 1 for each dose level. Again, the 90% CIs for the differences will be calculated and back-transformed.

Due to the scheme in dose escalation and the study design (parallel groups), the dose proportionality evaluation will be approached with a pure explorative intent. AUClast, Cmax and if the data permit AUC(0- τ) following repeat doses will be used for a preliminary assessment being aware the results should be interpreted with caution. The method foresees to apply the power model approach where the slope of the line obtained by regressing log(PK parameter) on log(dose) will be estimated and presented together with its 90% CI. Dose-proportionality implies a CI of regression coefficient (b as below) including 1 in the following model:

$$\log(\text{PK parameter}) = a + (b \cdot \log(\text{dose})) + \varepsilon$$

where a is the intercept, b the slope and ε the random error term.

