Reference: CS_WI_BS005

		
added:- Part A: T14.3.5.3, T14.3.5.4, T14.2.5.5, T14.2.5.6, F14.2.1.25, F14.2.1.26 and T14.1.21.2 modified.
 
Part B: T14.3.5.3, T14.3.5.4, T14.2.6.7, 14.2.9.2, F14.2.1.26, F14.2.1.27 and T14.1.22.2 modified.
 
3. The following suffix number are added to TFLs outputs to differentiate the study parts in CSR: .a added for Part A, .bi added for Part B IA and .bii added for Part B II.

--	--	--

Document: PPD

Author: PPD

Version Number:

V2.2

Version Date:

21 March 2018

Template No: CS_TP_BS016 – Revision 3

Reference: CS_WI_BS005

Effective Date: 01May2012

Copyright © 2012 Quintiles Transnational Corp. All rights reserved.

The contents of this document are confidential and proprietary to Quintiles Transnational Corp. Unauthorized use, disclosure or reproduction is strictly prohibited.

LIST OF ABBREVIATIONS AND DEFINITION OF TERMS

AE	Adverse Event
ALP	Alkaline phosphatase
ALT	Alanine aminotransferase
AST	Aspartate aminotransferase
ATC	Anatomical Therapeutic Chemical Classification
AUC	Area under concentration-time curve
AUC _(0-τ)	Area under concentration-time curve over the dosing interval: from t=0 to t=12h
AUC _{last}	Area under concentration-time curve over the dosing interval: from t= 0 up to the last detectable concentration timepoint
b.i.d.	Bis In Die (twice daily)
BLQ	Below the lower limit of quantitation
BUN	Blood Urea Nitrogen
Ca	Calcium
CI	Confidence Intervals
Cl	Chloride
Clast	Last detectable plasma concentration
Cmax	Maximal plasma concentration
cMPN	chronic Myelo-Proliferative Neoplasms
CMO	Contract Manufacturing Organization
CR	Complete Response
CRF	Case Report Form
CRO	Contract Research Organization
CT	Computerized Tomography
CTCAE	Common Terminology Criteria for AE
Cτ	trough concentration (Pre-dose levels on day 28 in the cycles of treatment)
CV	Coefficient of Variation
DLT	Dose Limiting Toxicity

Document: PPD

Author: PPD

Version Number:

V2.2

Version Date:

21 March 2018

Template No: CS_TP_BS016 – Revision 3

Reference: CS_WI_BS005

Effective Date: 01May2012

Copyright © 2012 Quintiles Transnational Corp. All rights reserved.

The contents of this document are confidential and proprietary to Quintiles Transnational Corp. Unauthorized use, disclosure or reproduction is strictly prohibited.

ECG	Electrocardiogram
ECOG	Eastern Cooperative Oncology Group
ELN	European LeukemiaNet
ET	Essential Thrombocythemia
EU	European Union
EUMNET	European Myelofibrosis Network
Hb	Haemoglobin

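### The AUClast accumulation ratio can be inflated in patients whose last quantifiable sample is later on Day 28 than on Day 1, and the metabolite/parent area ratio has no fixed-interval version

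*SAP*

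**What the plan says.** The SAP's list of abbreviations defines the two areas. AUClast is the "Area under concentration-time curve over the dosing interval: from t= 0 up to the last detectable concentration timepoint". AUC(0-tau) is the "Area under concentration-time curve over the dosing interval: from t=0 to t=12h".

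Section 18.3 then sets these rules:

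- **Tail of the profile.** "All BLQ values after the last detectable plasma concentration will be excluded". Areas use the linear trapezoidal rule.
- **Accumulation.** "Accumulation ratios Ro on Cmax, AUClast and if data permit on" AUC(0-tau), each as Day 28 divided by Day 1 within patient.
- **Inference on accumulation.** A mixed model on log-transformed values of the same metrics, with day fixed and patient random: "Day 28 will be compared vs Day 1 for each dose level", with 90% confidence intervals.
- **Metabolites.** "Ratios between metabolites (ITF-2374 and ITF-2375) to parent drug will be performed on Cmax and AUClast on day 1 and day 28".
- **Availability of the fixed-interval area.** The first parameter list gives AUC(0-tau) "if data permit and only for Givinostat". A second list in the same section omits the restriction to the parent, but the metabolite/parent sentence names only Cmax and AUClast either way.

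Tlast is itself a listed parameter. No rule requires the two areas in a ratio to end at the same time, and none says which accumulation metric leads if AUClast and AUC(0-tau) disagree.

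**The concern.** A ratio of two areas estimates accumulation, or relative exposure, only if both areas cover the same span. AUClast does not guarantee this. If the drug accumulates, Day 28 concentrations are higher and tend to stay above the assay limit longer. The Day 28 area can then include hours that the Day 1 area lacks, and the error runs in the same direction as the effect being estimated. The mixed model takes the same log AUClast values, and its 90% interval describes sampling variability, not this bias.

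For the metabolites, parent and metabolite are different analytes with no reason to share a Tlast, and AUClast is the only area planned for their ratio. Characterising PK is a secondary objective in both parts (SAP 2.2), so these ratios will be reported and read as estimates.

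**Working it through.** **Inputs.** From the SAP: the AUClast end point and the 12 h interval (list of abbreviations), and the BLQ and trapezoidal rules (18.3). The SAP states no accumulation figure, so there is nothing to reproduce. Half-life, assay limit, sampling times and Tlast are not given; all values below are assumptions for illustration.

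**Step 1. Bias in the accumulation ratio, mono-exponential decline.** With half-life h, the fraction of the single-dose area reached by time t is f(t) = 1 - 2^(-t/h). At steady state with 12-hourly dosing, concentrations are Rac = 1/(1 - 2^(-12/h)) times those of Day 1. The AUClast ratio is therefore Rac x f(Tlast Day 28)/f(Tlast Day 1), and the bias factor is f(Tlast Day 28)/f(Tlast Day 1). With Day 28 Tlast = 12 h:

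| h (h) | f(8) | f(10) | f(12) | Bias, Day 1 Tlast 8 h | Bias, Day 1 Tlast 10 h | True Rac |
|---|---|---|---|---|---|---|
| 3 | 0.843 | 0.901 | 0.938 | 1.113 | 1.041 | 1.067 |
| 6 | 0.603 | 0.685 | 0.750 | 1.243 | 1.095 | 1.333 |
| 9 | 0.460 | 0.537 | 0.603 | 1.311 | 1.123 | 1.658 |

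The inflation is 4% to 31%. If both areas end at the same time T, f(T) cancels and the ratio equals Rac exactly.

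**Step 2. What assay limit makes this happen?** For Tlast 8 h on Day 1 and 12 h on Day 28, the limit must lie above the Day 1 level at 12 h, 2^(-12/h). It must also be no higher than the Day 28 level at 12 h, Rac x 2^(-12/h), or the Day 1 level at 8 h, 2^(-8/h). As a percentage of the Day 1 peak:

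- h = 3: 6.25% to 6.67%. This also needs no 10 h sample, because Day 1 at 10 h is 9.9%, above the window.
- h = 6: 25% to 33%.
- h = 9: 40% to 54%.

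The 24% and 31% figures thus require an assay that loses the drug at a quarter to a half of its peak.

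**Step 3. Oral model with the SAP's own BLQ and trapezoidal rules.** Assumed: one compartment, absorption rate 1.5/h, samples at 0, 0.5, 1, 2, 3, 4, 6, 8 and 12 h, assay limit 2-40% of Day 1 Cmax.

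- Tlast equal on both days: the AUClast ratio is within 0.4% of the 0-12 h ratio.
- Half-life 4 h, limit 20%: Tlast 8 vs 12 h, 1.17 becomes 1.41 (+21%). Over a common interval it returns to 1.17.
- Half-life 4 h, limit 40%: Tlast 6 vs 8 h, +19%.
- Half-life 6 h, limit 40%: Tlast 8 vs 12 h, 1.38 becomes 1.77 (+29%).
- Half-life 2 h: Tlast was equal at every limit tried, so there was no material bias.

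**Step 4. Metabolite/parent, same oral model.** The metabolite is given the parent's shape at a lower level, with the assay limit at 5% of parent Cmax. When both reach 12 h the bias is zero. When the parent reaches 12 h and the metabolite only 6-8 h, the ratio is understated by 17% to 31%.

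**Step 5. Does cutting both analytes at the shorter Tlast cure it?** Not if their shapes differ. Take mono-exponential profiles, parent Tlast 8 h, metabolite Tlast 12 h, metabolite half-life 9 h, and the 0-12 h ratio as target. The bias factors come from Step 1.

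- Parent half-life 3 h: the AUClast ratio is off by 1.113, or +11%. Cutting both at 8 h gives 1.113/1.311 = 0.849, or -15%.
- Parent half-life 6 h: the AUClast ratio is off by +24%. Cutting both at 8 h gives 1.243/1.311 = 0.948, or -5%.

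Truncation can make matters worse or better, depending on profiles the SAP does not give.

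**The case against.** The strongest reply is that the problem is possible but not shown. With no assay limit, sampling times or half-life in the SAP, nobody can say from this document that Tlast differs between days in any patient. A reader might infer that the planned ratios do compare unequal spans; the text supports only that they can. This objection stands.

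The ratios also do not rest on AUClast alone. Cmax, which truncation does not touch, is planned for both, and AUC(0-tau) is planned for parent accumulation and its model where data allow. Tlast is already a listed parameter, so unequal end points could be noticed. That stands too, though the SAP neither ranks the metrics nor ties Tlast to the ratios.

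A reader might also infer that AUC(0-tau) will be absent exactly when truncation occurs. A profile below the limit before 12 h is an obvious candidate, but the SAP never defines when the data permit AUC(0-tau), so this is inference.

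Finally, one might say the artefact can equal the accumulation being estimated. In Step 1 that holds only at a 3 h half-life (11% against 7%), where the assay-limit window is a sliver. At 6 h and 9 h the artefact is smaller than the true accumulation (24% against 33%, 31% against 66%).

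**Conclusion.** The point holds as a conditional weakness of the stated method. The AUClast accumulation ratio and the mixed model on it are biased upward in any patient whose Day 28 Tlast is later than the Day 1 Tlast. The metabolite/parent area ratio has no fixed-interval check at all.

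The accumulation bias is about zero when Tlast is equal and roughly 4-31% when it differs, under the assumed models. In the oral model it arose only with the assay limit at 20-40% of Day 1 Cmax. How often it occurs in this trial cannot be judged from the SAP.

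Nothing beyond the PK description is affected. The MTD rests on Cycle 1 DLTs (17.1), the reasons listed in 3.7 for choosing the Part B dose do not include accumulation or metabolite ratios, and no threshold or hypothesis attaches to either ratio. It is worth correcting because the accumulation remedy is cheap and less biased: when Tlast is equal on both days, the fallback gives the same answer as AUClast.

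**What to change.** In SAP 18.3:

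1. Make AUC(0-tau) the lead area metric for Ro and for the mixed model, and state when the data are taken to permit it.
2. Where AUC(0-tau) is not available, compute both days' areas from 0 to the earlier of that patient's two Tlast values.
3. Keep AUClast as a descriptive parameter, and show Tlast by day and analyte beside any AUClast ratio.
4. For metabolite/parent, add AUC(0-tau) for ITF-2374 and ITF-2375 where data permit and use it for the ratio. Do not truncate both analytes to the shorter Tlast (Step 5).

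The cost is SAP wording, partial-area settings in the PK software and a little extra output; no new data are needed. The downsides are a shorter interval in some patients and a fallback interval that still depends on the assay limit. A patient sampled on only one day has no common interval, so cannot contribute to the fallback.

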3.4. TREATMENTS

3.4.1. TREATMENTS ADMINISTERED

Givinostat is supplied by the Sponsor or its designee as hard gelatine capsules for oral administration at the strength of 50 mg, and/or 75 mg, and/or 100 mg each.

Each capsule contains a granulate (obtained by wet granulation) composed of ITF2357, sodium starch glycolate, hydroxypropyl methyl cellulose (HPMC), sodium lauryl sulphate, lactose, magnesium stearate and colloidal silica.

The packaging consists of HDPE plastic bottles- closed with a PP screw cap, tamper evident - containing hard gelatine capsules of Givinostat. Each bottle contains:

- 30 capsules of 50 mg of Givinostat, or
- 30 capsules of 75 mg of Givinostat, or
- 15 capsules of 100 mg of Givinostat.

At each visit, patients receive a number of bottles sufficient to cover the period between two visits.

In **Part A** patients can be treated in DLs at the following starting daily doses of Givinostat:

Document: PPD

Author: PPD

Version Number:

V2.2

Version Date:

21 March 2018

Template No: CS_TP_BS016 – Revision 3

Reference: CS_WI_BS005

Effective Date: 01May2012

Copyright © 2012 Quintiles Transnational Corp. All rights reserved.

The contents of this document are confidential and proprietary to Quintiles Transnational Corp. Unauthorized use, disclosure or reproduction is strictly prohibited.

- 50 mg b.i.d.;
- 100 mg b.i.d.;
- 150 mg b.i.d.;
- 200 mg b.i.d.;
- 150 mg t.i.d.;
- 200 mg t.i.d..

Intermediate Dose Levels (IDLs) and, consequently, additional DLs can be used to establish the MTD (for more details, see [paragraph 4.1.1.3](#) of the Study protocol version 3.0).

Notably, the tested DLs to be considered for the MTD statistical analysis, are resumed in the **Table 1.1**.

Table 1.1 - Dose escalation of Givinostat performed in Part A

Givinostat daily dose	Givinostat dose level (DL)	DL used primarily to asses	Label for Tables, Listings and Figures (TLFs)
100 mg b.i.d.	DL1 (first three patients)	MTD, PK, PD	DL1
	DL1 (additional three patients)		DL1 expanded
2 capsules of 50 mg at the morning AND 1 capsule of 50 mg at the evening (i.e. 12 hours after)	DL6	MTD, PK, PD	DL6
50 mg b.i.d.	DL0	Safety, PK, PD*	DL0

* DL previously demonstrated as safe.

No patient will be treated at the DL2, none at DL3, none at DL4, none at DL5 in **Part A**, as per dose escalation scheme describe in the Study protocol and also summarised in the [section 3.2.2.1](#). of the present document.

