14. Update of the sections related to **Part B**, based on the definition of the MTD of Givinostat as chronic treatment in PV patients. Notably, in July 2015 the tolerability data related to the patients enrolled in **Part A** – i.e. the six patients treated at the Dose Level 1 (i.e. 100 mg b.i.d., DL1) and 3 patients treated at the Intermediate Dose Level (i.e. 150 mg/die, also defined

Document PPD

Author: PPD

Version Number:

V2.2

Version Date:

21 March 2018

Template No: CS_TP_BS016 – Revision 3

Reference: CS_WI_BS005

Effective Date: 01May2012

Copyright © 2012 Quintiles Transnational Corp. All rights reserved.

The contents of this document are confidential and proprietary to Quintiles Transnational Corp. Unauthorized use, disclosure or reproduction is strictly prohibited.

“DL6”) - have been considered in order to define the MTD of Givinostat as chronic treatment in PV patients. Even if only one DLT was observed in the 6 patients treated at DL1 during the first cycle of treatment (i.e. a “*grade ≥ 3 non-haematological toxicity*” (dyspepsia), judged “*drug-related*” by the Investigator) and the escalation at higher DLs could be possible, the Study team agreed unanimously to consider the DL1 (i.e. 100 mg b.i.d.) as MTD of Givinostat to be used in **Part B** as chronic treatment in PV patients, considering the following points:

- Givinostat was a chronic treatment for PV patients in the current schedule;
- The observed PLT decrease;
- The knowledge of the safety profile of HDACi and, in particular, of Givinostat (i.e. thrombocytopenia was a side-effect);
- It could be preferable/ethical to avoid exposing 3 patients to the higher dosage (i.e. 150 mg b.i.d., DL2) that, as above reported, will be reasonably untolerated by the patients.

Therefore, the dosage to use in **Part B** as established in **Part A** by the Study team, i.e. 100 mg b.i.d., was defined as the MTD of Givinostat taking into account the chronic schedule of the study drug as prescribed in this current study.

15. Update of the dose modification rules to be applied in **Part B** and in **Part A** for patients who may be allowed to escalate their Givinostat dose up to the MTD for the remainder of the Study (**Part A**) at the discretion of the Investigator and Sponsor.

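### SAP 18.3: a slope CI that includes 1 is the only stated criterion for dose proportionality, so an imprecise estimate can pass as proportional (low priority, wording fix)

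*SAP*

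**What the plan says.** Section 18.3 assesses dose proportionality with a power model, in which "the slope of the line obtained by regressing log(PK parameter) on log(dose") "will be estimated and presented together with its 90% CI". The model is log(PK parameter) = a + b·log(dose) + error. The single interpretive sentence is: "Dose-proportionality implies a CI of regression coefficient (b as below) including 1 in the following model".

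The same paragraph limits the weight of the result: "the dose proportionality evaluation will be approached with a pure explorative intent", and the exposure parameters "will be used for a preliminary assessment being aware the results should be interpreted with caution". It gives no limits for b, no maximum interval width and no third outcome between proportional and not proportional.

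Two other sections fix the data available from Part A. Section 3.4.1 (Table 1.1) lists only DL0 (50 mg b.i.d.), DL6 and DL1 (100 mg b.i.d.), and says "No patient will be treated at the DL2, none at DL3, none at DL4, none at DL5 in" Part A. DL6 is "2 capsules of 50 mg at the morning AND 1 capsule of 50 mg at the evening". Section 3.7 refers to "the six patients treated at the Dose Level 1 (i.e. 100 mg b.i.d., DL1) and 3 patients treated at the Intermediate Dose Level". No DL0 count is given.

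**The concern.** A 90% CI that includes 1 shows that a two-sided test at the 10% level did not reject b = 1. That is not evidence that b is close to 1. With few patients and a narrow dose range the interval is wide, and slopes well away from 1 remain compatible with the data.

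Over a two-fold dose range, b = 1 means exposure doubles (2^1 = 2), b = 1.5 means it rises 2.8-fold (2^1.5 = 2.83), and b = 2 means it rises four-fold. A PK report that took the sentence as its rule could call any of these proportional. The criterion also rewards imprecision: the noisier the data, the more often a non-proportional drug meets it. At stake is what the PK report may conclude about the dose–exposure relationship.

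**Working it through.** The SAP states no sample size, CV or operating characteristic for this analysis, so there is no figure of its own to reproduce. The check asks how often the criterion is met when proportionality does not hold.

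**Inputs from the SAP**
- 90% CI for b in the power model (18.3).
- Dose levels DL0, DL6 and DL1: 100, 150 and 200 mg per day (3.4.1), a ratio of 2.
- 6 patients at DL1 and 3 at DL6 (3.7).

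**Assumptions (not in the SAP)**
- 3 patients at DL0, varied from 1 to 6 below.
- Between-patient CV of 20%, 30%, 50% or 70%.
- Log-normal exposure with the same CV at each dose.
- Section 18.3 does not say whether dose means daily dose or the single administration, and DL6 has unequal morning and evening doses. Both were used: daily dose (3 at 100 mg, 3 at 150 mg, 6 at 200 mg) and morning administration (3 at 50 mg, 9 at 100 mg).

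**Formulas**
- σ = √ln(1 + CV²)
- Sxx = Σ(x − x̄)², with x = ln(dose)
- SE(b) = σ/√Sxx
- CI half-width ≈ t(0.95; n − 2) × SE(b)
- P(CI includes 1) = P(|T| < t(0.95; n − 2)), with T non-central t on n − 2 degrees of freedom and non-centrality (b − 1)/SE(b)

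**One case in full (daily dose, CV 50%, b = 1.5)**
- Sxx = 0.968 and σ = √ln(1.25) = 0.472.
- SE(b) = 0.472/√0.968 = 0.48.
- t(0.95; 10) = 1.812, so the half-width is about 1.812 × 0.48 = 0.87.
- Non-centrality = 0.5/0.48 = 1.04, which gives P = 0.745.

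On the morning-administration dose, Sxx = 1.081, SE = 0.45, half-width 0.82 and P = 0.73.

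**Probability that the 90% CI includes 1 (n = 12; morning-administration to daily dose)**

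| CV | b = 1 | b = 1.5 (or 0.5) | b = 2 | Typical half-width |
|---|---|---|---|---|
| 20% | 0.90 | 0.21–0.25 | about 0 | 0.35–0.37 |
| 30% | 0.90 | 0.50–0.53 | 0.05–0.07 | 0.51–0.54 |
| 50% | 0.90 | 0.73–0.75 | 0.34–0.38 | 0.82–0.87 |
| 70% | 0.90 | 0.80–0.81 | 0.54–0.58 | 1.10–1.16 |

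Each column away from b = 1 rises as precision falls. The limit is 0.90, because as SE(b) grows the non-centrality goes to 0.

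**Sensitivity (b = 1.5, daily dose)**
- DL0 count from 1 to 6: 0.71 down to 0.38 at CV 30%, and 0.82 down to 0.67 at CV 50%.
- Adding 28 Part B patients at 200 mg per day, with 3 at DL0: 0.65 at CV 50% and 0.35 at CV 30%. Most of the added patients sit at one dose, so they sharpen the slope only modestly.

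**If limits were set instead (illustration)**

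Exposure-ratio limits of 0.80 to 1.25 over a two-fold range give slope limits of 1 + ln(0.8)/ln 2 = 0.68 and 1 + ln(1.25)/ln 2 = 1.32. Suppose the whole 90% CI must lie inside them (daily dose, 3/3/6 patients). A truly proportional drug (b = 1) is then declared proportional with probability 0.81 at CV 10%, 0.07 at 20%, 0.003 at 30% and about 0 at 50%. For b = 1.5 the probability is 0.004 or less at every CV tried.

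**The case against.** The strongest defence is the text itself. Read literally, the sentence runs from proportionality to the interval: if exposure is proportional, the CI should include 1. The SAP never says that proportionality will be concluded when it does. What it commits to is an estimate with its 90% CI, in a paragraph that calls the work exploratory and asks for caution. Dose proportionality is not a listed objective (section 2.2 has only the characterisation of PK). The MTD rests on Cycle 1 DLTs and the study team's tolerability judgement.

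Much of this stands, and it sets the weight. It does not clear the sentence. No other criterion is offered, and the call for caution does not tell the report's author what to write when the interval is, say, 0.7 to 2.3.

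A reader might infer more than the SAP supports: that proportionality will be declared whenever the CI includes 1, that imprecision makes this nearly certain, or that the report would be wrong in most non-proportional cases. The first reads a decision rule into a sentence that states a necessary condition. The second ignores the 90% ceiling. The third depends on a CV that the SAP does not give: at CV 20% a slope of 1.5 passes only about 21–25% of the time, and a slope of 2 passes in a minority of cases even at CV 50%.

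It is also fair to object that equivalence limits would rarely be met with these data. They are therefore an option and not a requirement.

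**Conclusion.** The point holds as a low-priority defect of wording. Section 18.3 offers one criterion, which failure to exclude 1 satisfies, and provides no inconclusive outcome. In practice non-rejection would be likely to stand in for evidence of proportionality.

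The size depends on variability. With 3 patients assumed at DL0, a true slope of 1.5 goes undetected about a fifth to a quarter of the time at CV 20%, about half at CV 30%, and about three-quarters or more at CV 50% and above. The direction is the same whichever dose metric or DL0 count is used, and with or without Part B patients. The exploratory label and the caution wording reduce the importance but do not correct the criterion. Neither the MTD nor the primary efficacy analysis is affected.

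**What to change.** In section 18.3:

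1. Delete the sentence that links proportionality to a CI including 1, or restate it to say that a CI including 1 does not by itself establish proportionality.
2. Keep the planned estimate of b with its 90% CI, and add the fitted exposure ratio for a dose doubling (2^b, with its interval).
3. State that the result is inconclusive when the interval is wide.
4. Only if a verdict is wanted, require the whole 90% CI to lie within limits set in advance. The range 0.68 to 1.32 is one illustration for a two-fold dose range.

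The cost is wording in the SAP and the PK report, with no new data or analyses beyond a transformation of b. The downside of item 4 is that the answer will most likely be inconclusive, even for a drug that is truly proportional, unless between-patient variability is very low.
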